5.5. Analysis Visit Window and Therapy Periods

For all safety and efficacy parameters to be summarized or analyzed by visit, data records will be slotted to one of the protocol specified visits using the algorithm defined in [Appendix 3](#).

For classifying AEs (including hypoglycemic events), the therapy periods will be defined as pre-therapy, on-therapy and post-therapy. Albiglutide has a half-life of about 5 days in human body. Five times the half-life of a drug starting from the last dose of treatment is considered as the elimination period after which the drug has practically been eliminated from the system. Last dose date plus a period of 5 times of half-life of albiglutide, which

is within 25 days after the date of last dose, is defined as on-therapy window for subjects in the albiglutide arm. An AE is defined as on-therapy AE if the onset date is on or after the start date of randomized study medication and within last dose date plus 25 days in the albiglutide arm or within the last dose date in the lispro arm. For other safety parameters that are assessed prior to administration of randomized study medication on dosing days, the assessment date is used to determine the therapy periods. Details on the therapy periods of AEs and other safety parameters are provided in [Appendix 4](#).

5.6. Multiple Evaluations

After all the records have been slotted based on therapy period and study day, if there are multiple valid records for an assessment within an assigned analysis visit, only one of these records will be used for summary statistics and analyses. The record to be used is determined using the following hierarchy (in decreasing order of priority):

- the record closest to the target visit day
- the record with an original nominal visit that matches the analysis visit
- the record earliest in time for postbaseline assessments; for baseline, it is the record latest in time

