NOTE: If serum bilirubin fractionation is not immediately available, withdraw study medication for that subject if $ALT \geq 3 \times ULN$ and bilirubin $\geq 2 \times ULN$. Serum bilirubin fractionation should be performed if testing is available. If testing is unavailable, **record presence of detectable urinary bilirubin on dipstick**, indicating direct bilirubin elevations and suggesting liver injury.

- Complete the liver imaging and/or liver biopsy eCRFs if these tests are performed
- Perform liver event follow-up assessments and monitor the subject until liver chemistries resolve, stabilize, or return to baseline values as described below
- Withdraw the subject from the study (unless further safety follow-up is required) after completion of the liver chemistry monitoring as described below
- Do not restart investigational product

In addition, for criterion 1:

- Make every reasonable attempt to have subjects return to clinic within **24 hours** for repeat liver chemistries, liver event follow-up assessments (see below), and close monitoring
- A specialist or hepatology consultation is recommended
- Monitor subjects twice weekly until liver chemistries (ALT, AST, ALP, and bilirubin) resolve, stabilize, or return to within baseline values

For criteria 2, 3, 4, and 5:

- Make every reasonable attempt to have subjects return to clinic **within 24 to 72 hours** for repeat liver chemistries and liver event follow-up assessments (see below)
- Monitor subjects weekly until liver chemistries (ALT, AST, ALP, and bilirubin) resolve, stabilize, or return to within baseline values; criterion 5 subjects should be monitored as frequently as possible.

Subjects with $ALT \geq 5 \times ULN$ and $< 8 \times ULN$ that exhibit a decrease to $ALT \geq 3 \times ULN$, but $< 5 \times ULN$ and bilirubin $< 2 \times ULN$ without hepatitis symptoms or rash, and who can be monitored weekly for 4 weeks:

- Notify the GSK/PPD medical monitor within 24 hours of learning of the abnormality to discuss subject safety
- Can continue investigational product
- Must return weekly for repeat liver chemistries (ALT, AST, ALP, and bilirubin) until they resolve, stabilize, or return to within baseline values
- If at any time these subjects meet the liver chemistry stopping criteria, proceed as described above

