8.3.7.1. Chemistry, Hematology and Urinalysis

Laboratory parameters include the following tests: hematology, chemistry and urinalysis. Established or generally acknowledged methods, normal ranges, and quality control procedures will be supplied by Quest Diagnostics Clinical Laboratory for the study records.

Hematology parameters used in summaries include complete blood count with red blood cell indices, white blood cell count differential, and platelet count. Chemistry parameters (including lipids) used in summaries include glucose, blood urea nitrogen, creatinine, sodium, potassium, chloride, carbon dioxide, calcium, total protein, albumin, total bilirubin, direct bilirubin, alkaline phosphatase (ALP), ALT, aspartate aminotransferase (AST), gamma-glutamyltransferase, uric acid, magnesium, phosphorus, eGFR, total cholesterol, low-density lipoprotein cholesterol, high-density lipoprotein cholesterol, triglycerides. Urinalysis parameters used in summaries include specific gravity, pH, glucose, ketones, microalbumin, creatinine, blood, leukocyte esterase, and nitrites.

All laboratory parameters will be summarized, for each treatment group, at every scheduled assessment time point using descriptive statistics and presented graphically. In addition, for hematology and chemistry laboratory parameters, change from Baseline in these quantitative tests will be summarized by treatment group and at every scheduled assessment postbaseline time point. Shift tables providing the number and percentage of subjects with indicated shifts (normal, abnormal not of clinical concern, abnormal of clinical concern) in their results from baseline to each scheduled postbaseline assessment will also be presented for all hematology and chemistry parameters.

Additionally, the number of subjects with laboratory values of potential clinical concern will be summarized by treatment group and scheduled assessment time point for hematology and chemistry. The criteria for laboratory values of potential clinical concern are detailed in [Appendix 7: Values of Potential Clinical Importance](#).

A summary of laboratory values of potential clinical concern will be provided for liver function tests, including ALT, AST, and total bilirubin. The criteria for liver function

tests of potential clinical concern are detailed in [Appendix 7: Values of Potential Clinical Importance](#).

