11.3.2. Visit Slotting Algorithm

For all safety and efficacy parameters to be summarized or analyzed by visit, data records will be slotted to one of the protocol specified visits using the following algorithm:

- a) Determine the therapy period and study day for all records using the algorithms from Appendix 4: Treatment Periods.
- b) For all records (including unscheduled visit records, early withdrawal records and repeat visit records), use the therapy period and study day determined above with the slotting intervals in the Table Analysis Visit Windows below to slot the record to the appropriate analysis visit.
 - For records determined to be in the pre-therapy period, the Week -6 and Week -4 analysis visits will be based on the nominal visits recorded on the eCRF. The Week -1 and Baseline analysis visits will be assigned based on the study day slotting intervals as shown in the table below.
 - For records determined to be in the on-therapy period, use the study day with the slotting intervals in the table below to assign the records to the appropriate on-therapy analysis visit (Week 1 through Week 26).
 - For records determined to be in the post-therapy period, the study day will not be used for assigning the analysis visit. Instead, all post-therapy period records for subjects who complete randomized study treatment according to protocol will be assigned to the Week 30 post-therapy analysis visit. For subjects who terminate study treatment early, the follow-up analysis visit will be based on the nominal visit recorded on the eCRF. All other post-therapy period records for subjects who terminate study treatment early will be assigned to the 4 Week Follow-up analysis visit.

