11.3.4. Analysis Visit Windows

Table - Analysis Visit Windows

Scheduled Visit	Target Study Day of Visit	Slotting Intervals
Week -6	-42	Visit = " SCREENING"
Week -4	-28	Visit = " STANDARDIZATION 1"
Week -1	-7	Visit = " STANDARDIZATION 4"
Baseline (Week 0)	1	Visit = " BASELINE"
Week 4	29	2 to 32 days
Week 5	36	33 to 53 days
Week 10	71	54 to 99 days
Week 18	127	100 to 155 days
Week 26 (End of Treatment Visit)*	183	Albiglutide arm: 156 to (last dose date + 25 days) Lispro arm: 156 to last dose date
Week 30**	211	For subjects completed study Albiglutide arm: >Last dose date + 25 days Lispro arm: >Last dose date
4 Week Follow-up Visit**	Last dose date + 35 days***	For subjects didn't complete study Albiglutide arm: >Last dose date + 25 days Lispro arm: >Last dose date

* Week 26 is the end of treatment visit for those subjects completing the study per-protocol. For subjects who withdraw early from active treatment, the end of treatment visit will be assigned to an analysis visit based on the visit slotting algorithm using study day and therapy phase.

** Week 30 is the 4 week post-treatment follow-up visit for those subjects completing the study per-protocol. The 4 Week Follow-up Visit is the 4 week post-treatment follow-up visit for those subjects who withdraw early from active treatment. Both visits will be assigned based on the visit slotting algorithm using therapy phase.

*** The target study day for the 4 Week Follow-up Visit for subjects who withdraw early from active treatment is set to be 5 weeks (35 days) after last dose to correspond with the timing of the 4 week post-treatment follow-up for subjects completing the study per-protocol (where last dose is at Week 25 and the follow-up visit is at Week 30).

For parameters which were not scheduled to be collected at all visits, the all-inclusive visit intervals defined for all visits (that is, the visit window table above) will still be used to slot records. However, if a value is slotted to a visit unscheduled for a parameter, it will not be summarized (and not be included in the efficacy datasets) but will be included in data listings.

For analyses on the prescribed insulin dose, the total number of weekly insulin injections and SMBG profile, visit and visit dates recorded on the eCRF are used for analysis because a specific visit date is needed to calculate the analysis values.

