3.131	Safety		On-therapy and Post-therapy Potential System Allergic Reactions Identified by the Investigator		
3.132	Safety		On-therapy and Post-therapy System Allergic Reactions Identified by a Customized MedDRA Query		
3.133	Safety		Kaplan-Meier Analysis of Time to First Occurrence of On-therapy Systemic Allergic Reaction Reported by the Investigator		

Safety : Tables					
No.	Population	IDSL / TST ID / Example Shell	Title	Programming Notes	Deliverable [Priority]
3.134	Safety		Kaplan-Meier Analysis of Time to First Occurrence of On-therapy Systemic Allergic Reaction Identified by a Customized MedDRA Query		
3.141	Safety		On-therapy and Post-therapy Injection Site Reactions		
3.142	Safety		Kaplan-Meier Analysis of Time to First Occurrence of On-therapy Injection Site Reaction		
3.143	Safety		On-therapy Injection Site Reaction Over Time		
3.144	Safety		Summary Characteristics of On-therapy Injection Site Reactions Identified by the Investigator		
3.151	Safety		On-therapy and Post-therapy Liver Events Identified by a Customized MedDRA Query		
3.161	Safety		On-therapy and Post-therapy Pancreatitis and Pancreatic Cancer		
3.162	Safety		On-therapy and Post-therapy Adjudicated Pancreatitis Events		
3.171	Safety		On-therapy and Post-therapy Atrial Fibrillation and Atrial Flutter Adverse Events		
3.181	Safety		On-therapy and Post-therapy Pneumonia Adverse Events Reported by the Investigator		
3.182	Safety		On-therapy and Post-therapy Pneumonia Adverse Events Identified by a Customized MedDRA Query		
3.191	Safety		On-therapy and Post-therapy Diabetic Retinopathy Adverse Events		
3.201	Safety		On-therapy and Post-therapy Appendicitis Adverse Events		
3.211	Safety		On-therapy and Post-therapy Malignant Neoplasm Adverse Events Identified by a Customized MedDRA Query		

Safety : Tables					
No.	Population	IDSL / TST ID / Example Shell	Title	Programming Notes	Deliverable [Priority]
Labs					
3.221	Safety		Change from Baseline in Hematology by Visit		
3.222	Safety		Change from Baseline in Chemistry by Visit		
3.223	Safety		Hematology Values of Clinical Concern by Visit		
3.224	Safety		Chemistry Values of Clinical Concern by Visit		
3.225	Safety		Liver Function Tests of Clinical Concern by Visit		
3.226	Safety		Shift in Hematology by Visit		
3.227	Safety		Shift in Chemistry by Visit		
3.228	Safety		Urinalysis by Visit		
3.229	Safety		Change from Baseline to Week 26 in Urine Albumin/Creatinine Ratio (mg/mmol)		

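### The one-record-per-visit and unscheduled-visit rules can leave abnormal repeat, unscheduled and early-withdrawal safety values out of the clinical-concern tables

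*SAP*

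**What the plan says.** **Slotting.** SAP 11.3.2 applies "For all safety and efficacy parameters to be summarized or analyzed by visit". Its slotting instruction opens with "For all records (including unscheduled visit records, early withdrawal records and repeat visit records", so repeat and unscheduled safety results enter the same process as scheduled ones. SAP 11.3.3 assigns early-withdrawal safety results to a scheduled visit by the same algorithm.

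**Selection.** Where several records land in one analysis visit, SAP 5.6 states that "only one of these records will be used for summary statistics and analyses". The first criterion is "the record closest to the target visit day"; ties go to a matching nominal visit, then to the earliest postbaseline record. Safety data are not exempted.

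**Exclusion.** SAP 11.3.4 says that "if a value is slotted to a visit unscheduled for a parameter, it will not be summarized". Such a value goes to the listings only.

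**Displays.** SAP 8.3.7.1 says that "the number of subjects with laboratory values of potential clinical concern will be summarized by treatment group and scheduled assessment time point" for haematology and chemistry. Table 3.225 is titled "Liver Function Tests of Clinical Concern by Visit", and Tables 3.223, 3.224, 3.232 and 3.342 are also titled by visit. SAP 8.3.8.2 presents the QTc categories (Tables 3.345 and 3.346) by visit and treatment group. Neither the SAP text nor the display list specifies an any-time or worst-value row.

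**Retesting.** For liver stopping criterion 1, Protocol 6.3.6 orders: "Monitor subjects twice weekly until liver chemistries (ALT, AST, ALP, and bilirubin) resolve, stabilize, or return to within baseline values". For the other stopping criteria the repeats are weekly.

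**The concern.** Choosing the record nearest the target day suits by-visit means. It does not suit a count of subjects who ever crossed a safety threshold. Subjects with an abnormal result are the ones who get repeat and unscheduled tests, and subjects who leave early have their last safety assessment at an off-schedule time. Those records are the most likely to lose to a nearer sample, or to fall in a window where the parameter was not scheduled.

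At stake are the by-arm counts of ALT or AST at the multiples of ULN in SAP 11.7.1, the combined ALT and bilirubin criterion, and the haematology, creatinine, vital-sign and QTc concern values.

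**Working it through.** The plan states no figure on this point. The check follows the rules through the windows and the schedule.

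**1. Windows (SAP 11.3.4).** Length = last day − first day + 1.

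| Visit | Days | Length | Target day |
|---|---|---|---|
| Week 4 | 2–32 | 31 | 29 |
| Week 5 | 33–53 | 21 | 36 |
| Week 10 | 54–99 | 46 | 71 |
| Week 18 | 100–155 | 56 | 127 |
| Week 26 | 156 onward (28 days to Day 183) | 28 | 183 |

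Total for Days 2–183: 31 + 21 + 46 + 56 + 28 = 182.

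**2. Which rule acts on which parameter.** The schedule is Protocol Table 5, repeated in SAP 11.2.1. Its ECG row is partly broken in the text and is read here as Screening, Week 0, Week 26 and early withdrawal.

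- ALT, total bilirubin and creatinine are in the reduced panel at Weeks 4, 5 and 18 (footnote 18) and in the full panel at Weeks 10 and 26. Vital signs are taken at every visit. Days in unscheduled windows: 0 of 182. Only SAP 5.6 can remove a peak.
- AST is not in the reduced panel, and haematology is not sampled at Weeks 4, 5 and 18. Days in unscheduled windows: 31 + 21 + 56 = 108.
- ECG is scheduled on treatment only at Week 26. Days in unscheduled windows: 31 + 21 + 46 + 56 = 154, which is every day from 2 to 155.

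These are spans of calendar time in which a value would be excluded. They do not estimate the share of records lost.

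**3. SAP 5.6 on ALT.** The Week 10 window can hold about 46/7 ≈ 6 weekly or 2 × 46/7 ≈ 13 twice-weekly draws, and Week 18 about 56/7 = 8 or 16. One is kept from each window. Take assumed ALT values (× ULN) of 2.4 on Day 71, then repeats of 5.6 on Day 74, 6.8 on Day 78, 4.2 on Day 85, 2.6 on Day 92 and 1.9 on Day 99, with 1.0 to 1.2 at the other visits. All six fall in Days 54–99. Day 71 is the target day, so 2.4 is retained, and Table 3.225 counts the subject at ≥2 × ULN only. The maximum over all records is 6.8, which also meets ≥3 × and ≥5 ×.

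In this example ALT is below 5 × on Days 71 and 85, so the excursion above 5 × lasts less than 14 days. If bilirubin stays below 2 × ULN, there are no symptoms and weekly monitoring is possible, the table in Protocol 6.3.13 does not require liver event documents. The subject therefore need not be in the liver-event count either.

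A repeat is not always lost. If no scheduled sample exists in the window, or the repeat is nearer the target day, it is the record kept.

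**4. Early withdrawal.** An ECG at an early-withdrawal visit on Days 2–155 is slotted to Week 4, 5, 10 or 18, where ECG is unscheduled, so SAP 11.3.4 keeps it out of every summary. Early-withdrawal AST and haematology are lost in the same way on Days 2–53 and 100–155. SAP 11.12 assumes 15% early withdrawal or loss to follow-up: 0.15 × 794 ≈ 119 subjects. The documents do not give the timing of withdrawal or the split between the two.

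**5. On-therapy periods (SAP 11.4).** For lispro completers the last dose date is set to the Week 30 visit, about Day 211, so Week 30 values fall in the lispro Week 26 window. They sit 211 − 183 = 28 days from target and normally lose to the Week 26 record. For albiglutide the on-therapy period ends 25 days after the last dose: Week 25 is about Day 176, and 176 + 25 = 201. Week 30 values therefore keep their own visit. A row defined as any time on-therapy would normally count Week 30 laboratory values for lispro only.

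**The case against.** A reader might infer that serious signals disappear from the trial's evidence. The documents do not support that. Protocol 6.3.6 requires a liver event form for any stopping criterion, and ALT ≥3 × with bilirubin ≥2 × ULN (>35% direct) must be reported as an SAE. SAP 8.3.5.8 promises by-arm counts of liver events from that form and from a MedDRA query, although the display list names only the query table (3.151). SAEs and discontinuations for AEs have Tables 3.42 and 3.51. Protocol 6.3.8 has clinically significant laboratory and ECG abnormalities recorded as AEs. Listings 1, 2 and 42 to 44 are dedicated to values of clinical concern. A subject with ALT 3.2 × on Day 71, then ALT 9 × and bilirubin 2.5 × on Day 75, would stay in the ≥3 × row and would ordinarily be reported as an SAE. Only the higher rows and the combined row would miss this subject. All of this stands.

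A reader might also turn 108/182 = 59% and 154/182 = 85% into expected losses. They are shares of days, and the denominator can be argued. Over Days 2–201 or 2–211 they become 108/200 = 54% or 108/210 = 51%, and 154/200 = 77% or 154/210 = 73%.

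Two further defences are fair. One record per visit is coherent for a by-visit table, and nothing in SAP 5.6 forbids adding an any-time row. SAP 8.3.7.1 and 8.3.8 do not tie the liver, vital-sign and ECG concern counts to time points; that comes from the table titles. The mock shells are in a separate document, so an any-time row there cannot be ruled out.

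This limits the point but does not remove it. AE recording depends on judgement of clinical significance, the listings give no by-arm counts, and the SAP itself specifies no such row.

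**Conclusion.** The point holds. Followed as written, SAP 5.6 and 11.3.4 can make the by-arm threshold counts in Tables 3.223 to 3.225, 3.232, 3.342, 3.345 and 3.346 too low. For ALT, total bilirubin, creatinine and vital signs this happens only through the one-record rule. AST, haematology and ECG are exposed to both rules.

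The size in subjects is unknown; it depends on how often subjects are retested and when they withdraw. The documents do not show that the undercount favours either arm. The different on-therapy definitions mean only that equality between arms cannot be assumed. The efficacy analyses are not affected. The conclusion rests on the visit schedule as read above and on the shells containing no any-time row.

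**What to change.** 1. State that SAP 5.6 and the unscheduled-visit exclusion in 11.3.4 apply only to efficacy data and by-visit summaries.
2. Add a row for any time post-baseline (worst value) to Tables 3.223 to 3.225, 3.232, 3.342, 3.345 and 3.346, using all scheduled, unscheduled, repeat and early-withdrawal records.
3. Use the same follow-up window in both arms for that row, for example through the Week 30 or 4-week follow-up visit, and not the arm-specific on-therapy definition in SAP 11.4.
4. For the combined liver row, evaluate ALT and bilirubin from all records, with a stated rule for pairing them in time.
5. Keep the by-visit rows.

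The cost is SAP wording and one extra row per table, from data already held. The drawback is that worst-value counts depend partly on how often subjects are retested, so they should be read beside the by-visit rows.

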6. STUDY POPULATION ANALYSES

6.1. Overview of Planned Analyses

The study population analyses will be based on the population specified in Section 4.

Table 2 provides an overview of the planned study population analyses with full details of data displays being presented in [Appendix 14: List of Data Displays](#).

Table 2 Overview of Planned Study Population Analyses

Display Type	Format		
	Figure	Table	Listing
Randomization			
Randomization			Y
Subject Disposition			
Subject Disposition		Y	Y
Reasons for Screening Failures and Standardization Failures		Y	Y
Reasons for Withdrawal from Study		Y	Y
Reasons for Discontinuing Study Treatment		Y	Y
Protocol Deviations		Y	Y
Deviations Leading to Exclusions from PP Population		Y	Y
Inclusion and Exclusion Criteria Deviations		Y	Y
Demography			
Demographics and Baseline Characteristics		Y	Y
Race & Racial Combinations		Y	Y
Substance use		Y	Y
Study Populations		Y	Y
Medical Condition & Concomitant Medications			
Medical Conditions (Current/Past)		Y	Y
Concomitant Medication		Y	Y
Exposure and Treatment Compliance			
Treatment Compliance		Y	Y
Exposure to Study Drug		Y	Y
Dose Titration			
Dose Titration			Y

Note: additional tables, listings and figures will be provided in [Appendix 14: List of Data Displays](#).

6.2. Disposition of Subjects

The number of subjects who were randomized and the number of subjects within each population (Full Analysis, Safety, Per- Protocol) will be summarized for each treatment group. A summary of subjects randomized by geographic region, country, and site will also be provided by treatment group.

The numbers and percentages of subjects who completed the study, discontinued the study, and discontinued the study treatment, along with reasons for discontinuation, will be summarized by treatment group.

A subject status by visit summary will be provided.

Subject disposition data will be listed as well. All disposition summaries will be based on all randomized subjects (i.e., FA Population).

